4.2 Emergency Department Visits

The ED visits endpoint will be defined as the time to first ED visit with the associated estimand being the hazard ratio from a recurrent time-to-event analysis. Emergency department visits will be identified from Medicare Outpatient claims files using the HCPCS codes for evaluation and management of a patient seen in the ED without further admission to the hospital (HCPCS codes: 99281-99285) and from the MedPAR (year 2016) and Inpatient files (years 2017-2019) as claims with revenue center codes 0450-0459, 0981 or a hospital inpatient claim with an emergency room charge>\$0. Emergency department visits will be identified from CMS Medicaid Professional claims with revenue service codes 99281-99285. ED visits will be identified from the BCBS Professional and Facility claims with place of service code=23 and the following revenue service codes: 0450', '0451', '0452', '0456', '0459', '0981','450', '451', '452', '456', '459', '981','00450', '00451', '00452', '00456', '00459', '00981'. Patients will be administratively censored one year after index hospitalization discharge.

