Secondary Outcome	Readmissions	30-day, 90-day and 1- year all-cause readmission	Approximately 1 year post-stroke in Phase 1	This will be collected via Administrative Claims Data sets from Medicare, Medicaid, and Blue Cross Blue Shield
Secondary Outcome	Mortality Mortal	ity	Approximately 1 year post-stroke in Phase 1	This will be collected via Administrative Claims Data sets from Medicare, Medicaid, and Blue Cross Blue Shield
Secondary Outcome	Emergency Department (ED) Visits	Number of patient emergency department visits	Approximately 1 year post-stroke in Phase 1	This will be collected via Administrative Claims Data sets from Medicare, Medicaid, and Blue Cross Blue Shield
Secondary Outcome	Admissions to skilled nursing facilities and inpatient rehabilitation facilities	Number of patient admissions and number of days in to skilled nursing facilities, and number of patient admissions to inpatient rehabilitation facilities	Approximately 1 year post-stroke in Phase 1	This will be collected via Administrative Claims Data sets from Medicare, Medicaid, and Blue Cross Blue Shield
Secondary Outcome	Use of transitional billing codes	Use of Transitional Care Management (TCM) billing codes and Chronic Care Management (CCM) billing codes	Approximately 1 year post-stroke in Phase 1	This will be collected via Administrative Claims Data sets from Medicare, Medicaid, and Blue Cross Blue Shield

Clinical Data collection:

• We will collect clinical data to inform the patient's individualized care plan that will be routine for implementing transitional care, and would like to keep this data for future analyses:

- Caribrioliai (Measure	Assessment(s)	When Collected	Appendix
Data collected to support the operations of the trial.	Neurological Status and Deficits	Post Stroke Advanced Practice Assessment	7-14 Day Visit	19
Data collected to support the operations of the trial.	Stroke Complications	Post Stroke Advanced Practice Assessment	7-14 Day Visit	19
Data collected to support the operations of the trial.	Stroke Risk Factor Management	Post Stroke Advanced Practice Assessment	7-14 Day Visit	19
Data collected to support the operations of the trial.	Lifestyle Coaching	Post Stroke Advanced Practice Assessment	7-14 Day Visit	19
Data collected to support the operations of the trial.	Medication Access and Use	Post Stroke Functional Assessment	7-14 Day Visit	17

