4 ENDPOINTS

Table 1 describes the set of outcomes and associated endpoints to be analyzed as a part of the claims analyses described in this statistical analysis plan. For each outcome, the data source, endpoint, reference period for which the endpoint is defined, and estimand are provided. For ITT analyses, the estimand defines a comparison between the COMPASS Intervention arm and the UC arm.

Table 1. Endpoints for Claims and Mortality Analysis				
Source	Outcome	Endpoint	Reference Period	Estimand
Claims	All Cause Hospital Readmissions	Incidence	30-days post index hospitalization discharge (unplanned)	Odds Ratio
		Incidence	90-days post index hospitalization discharge (unplanned)	Odds Ratio
		Time-to-hospital readmission	1-year post index hospitalization discharge	Hazard Ratio from recurrent events model
	Recurrent Stroke Hospital Readmissions	Time-to-recurrent stroke	1-year post index hospitalization discharge	Hazard Ratio from recurrent events model
	Emergency Department Visits	Time-to-first emergency department visit	1-year post index hospitalization discharge	Hazard Ratio
	Admission to Skilled Nursing/Inpatient Rehab Facility	Time-to first SNF/IRF admissions	1-year post index hospitalization discharge	Hazard Ratio
	Continuity of Care	Time-to-first visit with any provider	1-year post index hospitalization discharge	Hazard Ratio
	TCM Billing	Incidence	14-days post index hospitalization discharge	Odds Ratio
Claims & Mortality Index	All-Cause Mortality	Time-to-death by any cause	1-year post index hospitalization discharge	Hazard Ratio

Specific details regarding the definition of the endpoints is given subsequently in Section 4. Details regarding the analysis populations for the Phase 1 and Phase 2 analyses is given in Section 5. Specific details on statistical analysis methodology for endpoints having a common estimand (e.g., an odds ratio) are described in Section 6 as is general statistical methodology pertinent to all analyses.

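### The Medicaid ED-visit rule may miss visits that end in admission, which the Medicare rule counts under the same endpoint label

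*SAP*

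**What the plan says.** The Protocol's table of claims-linked outcomes (Data Collection and Outcome Measures) gives the outcome as "Number of patient emergency department visits" and does not split visits by whether the patient was admitted. SAP Table 1 gives "Time-to-first emergency department visit" over one year with a hazard ratio, again without a split. SAP 5.1 then analyses FFS Medicare, NC Medicaid and BCBS-NC as separate strata.

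SAP 4.2 sets out three identification rules:

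- **Medicare, Outpatient files:** codes for "a patient seen in the ED without further admission to the hospital (HCPCS codes: 99281-99285".
- **Medicare, inpatient files, in addition:** visits "from the MedPAR (year 2016) and Inpatient files (years 2017-2019) as claims with revenue center codes 0450-0459, 0981", with a non-zero ED charge on an inpatient claim as the alternative.
- **Medicaid:** "Emergency department visits will be identified from CMS Medicaid Professional claims with revenue service codes 99281-99285". Nothing further is listed.
- **BCBS:** "ED visits will be identified from the BCBS Professional and Facility claims with place of service code=23" together with a list of ED revenue codes.

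SAP 6.3.2, which covers time to ED visit, censors at death, at the first break in coverage, or administratively. It has no rule for an admission through the ED. Nothing in the SAP aligns the three rules, explains the Medicaid restriction or plans a sensitivity analysis for it. The remark that codes differ by claim type is made in 4.3, for SNF and IRF admissions only.

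**The concern.** The two Medicare sources together cover visits that end in discharge and visits that end in admission. The Medicaid rule keeps only the code range that the SAP itself ties to visits without admission. Taken at face value, a Medicare patient admitted through the ED has an event that day. The same patient in Medicaid has none and remains in the risk set, possibly until a later treat-and-release visit.

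Two things would follow. Events would be lost in the Medicaid stratum. Its hazard ratio would also describe a narrower endpoint than its label and than the Medicare hazard ratio reported under the same name. This matters if the intervention acts differently on the two kinds of visit. That is plausible, since readmission is itself a named outcome of the trial.

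The Medicaid sentence has a second fault. It calls 99281-99285 revenue codes, although the Medicare sentence correctly treats them as HCPCS codes. A programmer following it literally could search the wrong field.

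**Working it through.** The documents give no ED rate, admitted share, effect size or power for this endpoint, so there is no planned figure to reproduce. The first step compares the rules; the second is an illustration on assumed inputs.

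**Step 1. Which visits count, from SAP 4.2**

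| Payer | Claim source | Codes | Visit ending in admission counted? |
|---|---|---|---|
| Medicare | Outpatient and MedPAR/Inpatient | 99281-99285; or ED revenue codes or ED charge on an inpatient claim | Yes, through the inpatient source |
| Medicaid | Professional only | 99281-99285 | No, if the description given for Medicare Outpatient files carries over; otherwise not stated |
| BCBS | Professional and Facility | Place of service 23 and ED revenue codes | No restriction stated |

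**Step 2. Effect on the hazard ratio**

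Assume constant hazards for treat-and-release visits (TR) and visits ending in admission (AD). Let s be the share of the control-arm ED hazard that ends in admission. Then

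HR(any ED) = (1 − s) × HR_TR + s × HR_AD, and HR(treat-and-release only) = HR_TR.

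The shares and effects below are assumptions.

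| Scenario | s = 20% | s = 35% | s = 50% | Treat-and-release only |
|---|---|---|---|---|
| HR_TR 1.00, HR_AD 0.80 | 0.96 | 0.93 | 0.90 | 1.00 |
| HR_TR 1.15, HR_AD 0.80 | 1.08 | 1.03 | 0.98 | 1.15 |
| HR_TR 0.85, HR_AD 0.85 | 0.85 | 0.85 | 0.85 | 0.85 |

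For example, in the first row at s = 35%: 0.65 × 1.00 + 0.35 × 0.80 = 0.93.

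A fourth scenario lets the intervention turn 20% of admitted visits into treat-and-release visits. The any-ED ratio is then 1.00, and the treat-and-release ratio is 1 + 0.2s/(1 − s). This is 1 + 0.06/0.70 = 1.09 at s = 30% and 1 + 0.10/0.50 = 1.20 at s = 50%.

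**Step 3. Events lost**

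If a proportion c has any ED visit within a year, treat-and-release counting records 1 − (1 − c)^(1 − s).

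| c | s = 20% | s = 35% | s = 50% |
|---|---|---|---|
| 30% | 24.8% | 20.7% | 16.3% |
| 50% | 42.6% | 36.3% | 29.3% |

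At c = 30% the relative loss runs from (30 − 24.8)/30 = 17% to (30 − 16.3)/30 = 46%. Steps 2 and 3 apply only if Medicaid Professional claims omit admitted visits entirely. Partial capture gives intermediate values.

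**The case against.** The strongest reply is that the description of 99281-99285 as care without admission appears once, in the clause on Medicare Outpatient files. The Medicaid sentence uses Professional claims and does not repeat it. SAP 3.1 lists Inpatient, Outpatient and Physician files as separate categories, and nothing says that a professional ED claim is absent when the patient is admitted. This stands. A reader might infer that the Medicaid analysis certainly counts treat-and-release visits only, but the documents leave that open. They do not show the opposite either, so 4.2 has to say which applies.

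Second, a reader might infer that the Medicaid comparison of arms is biased. It is not, by this alone: both arms use the same rule, the strata are not pooled, and no contrast between payers is planned. The strata also differ by design, since dual enrollees are excluded from Medicaid and Medicare enrollees from BCBS.

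Third, admissions through the ED can appear in the readmission endpoints, which are also analysed for each payer. That is true and limits the loss of information, but it does not make the ED endpoint match its label.

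Fourth, the ratios of 1.09 and 1.20 might be read as a forecast of apparent harm. They arise only in the assumed conversion scenario; with equal effects on both visit types the definitions agree.

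Finally, the BCBS rule is worded differently again, but it states no limit on admission and no loss of BCBS visits is shown.

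**Conclusion.** The point holds in conditional form. SAP 4.2 builds one labelled endpoint from different event rules, and the Medicaid rule has no facility or inpatient source and a wrong code label. If the SAP's description of 99281-99285 extends to Medicaid Professional claims, the Medicaid stratum loses events and estimates a treat-and-release hazard ratio instead of the stated any-visit one. If those claims also capture admitted patients, the difference is smaller.

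The size cannot be derived from the documents. The illustrative gap is none when the effect is the same on both visit types, and 0.90 against 1.00 when half of visits end in admission and only those are reduced by 20%. The consequence is lost events and a mismatch between label and estimand on a secondary endpoint.

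This is separate from 4.2 naming a recurrent-event hazard ratio for what Table 1 and 6.3.2 treat as a first event. The event rule needs settling under either.

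**What to change.** In SAP 4.2:

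1. State that the event is any ED visit, whether or not it ends in admission.
2. For Medicaid, relabel 99281-99285 as HCPCS codes.
3. For Medicaid, add as an *or* condition facility and inpatient claims with ED revenue codes 0450-0459 or 0981, de-duplicated by date.
4. If the Medicaid files cannot support this, label that stratum's endpoint *ED visit without admission*, and add a Medicare sensitivity analysis that uses the Outpatient-file rule alone.

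The BCBS rule can stay as it is.

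The cost is a few lines of text, one extra claim selection and the matching of professional and facility claims for the same visit. The SAP already uses Medicaid facility claims for observation stays (4.1) and provider visits (Appendix A), and 3.1 lists inpatient files among the claims data. If Professional claims already capture admitted visits, the added sources do no harm once duplicates are removed.

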4.3 Admission to a Skilled Nursing Facility or Inpatient Rehabilitation Facility

The skilled nursing facility (SNF) and inpatient rehabilitation facility (IRF) endpoint will be defined as the time to the first admission to a SNF or IRF with the associated estimand being the hazard ratio from a time-to-event analysis. Patients will be administratively censored one year after index hospitalization discharge. The typical process for admission to a SNF or IRF is depicted in Figure 1.

COMPASS participants were discharged to the community following their index stroke event and the vast majority of SNF and IRF admissions will occur following a hospital discharge from a subsequent readmission (i.e., +/- 1 day) although we will identify any SNF or IRF admissions that occur after community discharge without a readmission. SNF and IRF admissions will be identified based on provider codes. The actual variable names and codes used to identify these events will vary depending on the claim type (i.e., Medicare, Medicaid, BCBS). SNF admissions will include swing bed stays.

Figure 1. Post-Acute Care Utilization after Hospital Readmission

4.4 Continuity of Care

The continuity of care endpoint will be defined as the time to the first outpatient ambulatory care visit with any provider. The associated estimand will be the hazard ratio from a time-to-event analysis. Patients will be administratively censored one year after index hospitalization discharge. In Medicare claims, ambulatory visits will be identified from Carrier claims using Evaluation and Management HCPCS codes for new or established office visit, consultation, or new/established preventive medicine visit. Additionally, we will use revenue center codes (0510-050521, 0523, 0526, 0529) from the Outpatient claims to identify visits to federally qualified health centers, rural health centers and other health clinics. For descriptive purposes, we will use physician specialty codes to classify providers as primary care physicians (including general practice, family practice, internal medicine, geriatric medicine, nurse practitioner, and multispecialty/group practice) as well as specialty codes in the Medicaid and BCBS Professional claims as well as facility names to identify qualifying primary specialty care providers (**Appendix A**).

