4.5 Transitional Care Management Billing

According to CMS guidelines,³ transitional care management (TCM) requires four core components: (1) transition in care from an inpatient setting to a community setting; (2) receipt of communication from a provider (direct contact, telephone, or electronic) within 2 business days of discharge; (3) moderate or high complexity medical decision making; and (4) a face-to-face clinical visit within 7 or 14 calendar days of discharge from the inpatient setting.

The TCM billing endpoint will be defined as incidence of TCM billing with the associated estimand being the odds ratio from a logistic model. Transitional care management billing is defined as an office visit billing through Current Procedural Terminology (CPT) codes 99495 (for a visit within 14 days of index hospitalization discharge) and 99496 (for a visit within 7 days of index hospitalization discharge). Because TCM billing codes became effective under Medicare's Physician Fee Schedule, and BCBS and Medicaid may not consistently use these codes, this endpoint will be defined for FFS Medicare participants only. The 30-day TCM eligibility period begins on the beneficiary's inpatient discharge date and continues for the next 29 days. Medicare beneficiaries who die or who have a hospital readmission within 30 days following the index discharge are not eligible to have a TCM claim. Therefore, even if they received TCM core components, such patients do not meet the TCM billing criteria. Because TCM billing can be rendered by physicians and non-physician practitioners in inpatient and outpatient setting, our assessment of TCM code billing will include claims from all practitioners.

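### The continuity-of-care visit list omits TCM codes 99495 and 99496, so a first visit billed only as TCM is missed or dated late

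*SAP*

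**What the plan says.** SAP Table 1 gives the continuity-of-care endpoint as "Time-to-first visit with any provider", analysed by a hazard ratio over one year. SAP 4.4 captures visits by two routes:

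- Carrier claims, through "Evaluation and Management HCPCS codes for new or established office visit, consultation, or new/established preventive medicine visit".
- Revenue center codes on Outpatient claims, "to identify visits to federally qualified health centers, rural health centers and other health clinics".

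Appendix A lists the HCPCS ranges 99201-99205, 99211-9215 (read here as 99211-99215), 99241-99245, 99385-99387 and 99395-99397. It also lists revenue codes 520, 521, 0510, 0517, 0519, 0523 and 0529.

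SAP 4.5 deals with TCM: "Transitional care management billing is defined as an office visit billing through Current Procedural Terminology (CPT) codes 99495" for a visit within 14 days, and 99496 for a visit within 7 days. One required component is "a face-to-face clinical visit within 7 or 14 calendar days of discharge from the inpatient setting". Patients "who die or who have a hospital readmission within 30 days following the index discharge are not eligible to have a TCM claim". The TCM period starts at the "inpatient discharge date and continues for the next 29 days". On payers it says "BCBS and Medicaid may not consistently use these codes, this endpoint will be defined for FFS Medicare participants only".

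The protocol's account of the Phase 1 intervention hospitals adds a visit at 7 to 14 days and describes the care process as in line with the CMS TCM codes.

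**The concern.** Two adjacent SAP sections treat the same claim differently. For the TCM endpoint, a 99495 or 99496 claim is an office visit. For continuity of care, which should count a visit with any provider, it is not. No reason is given.

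The omitted claim type is also the one closest to the intervention. If TCM-only first visits are more common in COMPASS, part of the earlier contact that the intervention is meant to produce is removed, and the hazard ratio (above 1 means earlier contact) is pulled down. If they are more common in usual care, it is pulled up. The TCM-billing endpoint will show whether billing differs by arm, but not how many first visits were lost or dated late.

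SIS-16, readmission and mortality are unaffected.

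**Working it through.** **Code check.** Neither 99495 nor 99496 lies in any of the five HCPCS ranges of Appendix A; the highest listed code is 99397. The omission follows from the text.

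**When a visit is lost.** All three must hold: the visit is billed as TCM on a professional claim with no separate listed E/M claim; no listed revenue code appears for it; and no listed visit came earlier. The patient is then dated at the next listed visit, or censored if there is none within the year.

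**Size.** The documents give no visit rate, TCM rate or power for this endpoint, so there is no plan figure to reproduce. Every input below is an assumption.

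- Ordinary (listed) visits: exponential, usual-care (UC) median 21 days; COMPASS the same unless stated.
- Early visit, uniform on days 7 to 14: 35% of COMPASS, 15% of UC.
- A share *s* of early visits is billed only as TCM, net of patients who cannot have a TCM claim.
- Revenue-code capture zero unless stated.
- Cox model, censored at 365 days; deaths and coverage breaks ignored; 1.5 million patients per arm.

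The proportion of patients with a TCM-only first visit is P(early visit) × *s* × P(ordinary visit comes later). The last term is the average of 2^(−v/21) over days 7 to 14:

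21/(7 ln 2) × (2^(−1/3) − 2^(−2/3)) = 4.328 × (0.7937 − 0.6300) = 0.709.

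At *s* = 30% this gives 0.35 × 0.30 × 0.709 = 7.4% of COMPASS and 0.15 × 0.30 × 0.709 = 3.2% of UC.

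| TCM share, both arms | TCM-only first visits, COMPASS / UC | True HR | Observed HR | Change |
|---|---|---|---|---|
| 10% | 2.5% / 1.1% | 1.18 | 1.16 | −1.8% |
| 20% | 5.0% / 2.1% | 1.18 | 1.14 | −3.6% |
| 30% | 7.4% / 3.2% | 1.18 | 1.12 | −5.3% |
| 50% | 12.4% / 5.3% | 1.18 | 1.08 | −8.3% |

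Percent changes come from unrounded hazard ratios. A repeat run agreed within 0.01.

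**Variations**

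- *Scheduled primary care visits shorten the COMPASS ordinary-visit median to 18, 16 or 14 days (30% share):* 1.33 becomes 1.27, 1.47 becomes 1.41, 1.64 becomes 1.59.
- *Revenue codes catch half of TCM visits in both arms:* 1.18 becomes 1.15 (30% share) or 1.12 (50% share). Full capture leaves no bias.
- *UC bills TCM more often, COMPASS share 30%:* the bias vanishes at a UC share of about 80% (0.15 × 0.80 × 0.709 = 8.5% TCM-only first visits in UC). At 100%, 1.18 becomes 1.21.
- *Equal early visits (35%), UC share 50%, COMPASS share 25%:* 1.00 becomes 1.07.
- *Codes added, 30% share, by date rule:* 1.18 if dated at the visit, 1.17 at day 14, 1.15 at day 29.

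**A second set of assumptions** gives larger shifts. It uses a control median of 14 days and a next listed visit 30 to 60 days later on average. TCM-only shares of visits by day 14 are 5% in UC and 20% to 40% in COMPASS. A true 1.30 is then observed as 1.10 to 0.78. With equal 20% shares, a true 1.00 stays at 1.00 and 1.30 becomes 1.22 to 1.16.

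**The case against.** The strongest reply is that neither size nor direction is established. That stands: the two sets of assumptions give very different shifts, and no document supplies any of the inputs.

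Revenue-code capture may also differ by arm. The 2-day call script (protocol Appendix 16) books COMPASS patients into the hospital's own stroke clinic, whose visits may produce a facility claim with a listed code. At a 30% TCM share with no capture in UC, 50% capture in COMPASS leaves TCM-only first visits at 7.4% × 0.5 = 3.7% against 3.2%, and 1.18 becomes about 1.16. At 80% capture they are 7.4% × 0.2 = 1.5% against 3.2%, and the ratio rises to about 1.20. This stands as a second route to reversal. It does not rescue the code list, because a visit seen only on a Carrier claim cannot be found in Outpatient claims.

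Other limits are also fair. The coordinator arranges primary care visits that the list would capture. The baseline hospital survey (protocol Appendix 2) asks about existing TCM billing, so usual-care hospitals may bill it too. The day-29 date is only a bound: SAP 4.5 gives the length of the period but does not say that a claim carries its last day.

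A broad reading of office visit might be thought to cover TCM, but Appendix A lists the codes and has no TCM row. Continuity of care is absent from the protocol's claims-outcome table, but the protocol's Analytical Plan names it among the secondary outcomes.

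**Conclusion.** The concern holds. Followed as written, SAP 4.4 and Appendix A miss or late-date a claim that SAP 4.5 itself counts as an office visit. With equal TCM shares and equal capture, the assumed base case lowers a true hazard ratio of 1.18 by about 2% to 8%. Other plausible inputs give no bias, a reversal or a larger shift. Direction depends mainly on which arm has more first visits seen only through TCM, after revenue-code capture; the documents do not say.

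The effect is confined to one secondary endpoint, mainly in the fee-for-service Medicare stratum. It bears on Phase 1 and the Phase 2 pre-post comparison. SAP 5.2 also applies every Table 1 endpoint to the sustainability comparison, so the same rule operates there. The change should be made, but it does not touch the trial's main conclusions.

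**What to change.** Make one SAP change:

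1. Add CPT 99495 and 99496 to the qualifying visit codes in SAP 4.4 and Appendix A for fee-for-service Medicare, and for Medicaid and BCBSNC where those payers use them.
2. State which claim date is the visit date for a TCM claim. If the face-to-face date cannot be read from the claim, cap the date at the latest day that SAP 4.5 allows: day 14 for 99495, day 7 for 99496. The cap assigns some event times and can cluster them, so report how often it is used.
3. Keep the current code list as a sensitivity analysis, with the number of TCM-only first visits by arm. That replaces the assumptions above with data.
4. Reconcile the revenue codes: as printed, 0526 is in SAP 4.4 but not in Appendix A.

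The cost is SAP wording, two codes and one date rule in the extraction program. The codes are already extracted for Medicare for the TCM endpoint; Medicaid and BCBSNC need a small added extraction. No new data collection is needed.
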